4. STATISTICAL METHODS

4.1. Sample Size Justification

Approximately 126 patients will be randomized to either edasalonexent or placebo in a 2:1 ratio. Based on Phase 1/2 data of changes in NSAA in this age group, an effect size of 0.625 is assumed. With this effect size, and assuming a dropout rate of approximately 20%, the study has approximately 80% power to show a difference between the treatment groups at a 2-sided type I error rate of 0.05.

Based on an underlying standard deviation estimate of 4.8 in the change from baseline in NSAA score (derived from the phase 2 study data) this would equate to a treatment difference of 3.0, which would be considered a clinically meaningful change.

4.2. General Statistical Methods and Data Handling

4.2.1. General Methods

Tabulations will be produced for appropriate demographic, Baseline, efficacy, and safety parameters. For categorical variables, summary tabulations of the number and percentage within each category (with a category for missing data) of the parameter will be presented. For continuous variables, the mean, median, standard deviation, minimum and maximum values will be presented. Unless otherwise defined for a particular endpoint, a patient's Baseline value is defined as the last non-missing measurement prior to the initiation of study drug. The first day of study drug is "Day 1".

Formal statistical hypothesis testing will be performed on the primary and secondary efficacy endpoints ([Section 2.5.1](#)), with all tests conducted at the 2-sided, 0.05 level of significance. Summary statistics will be presented, as well as confidence intervals (CIs) on selected parameters, as described in the sections below.

4.2.2. Computing Environment

All descriptive statistical analyses will be performed using SAS statistical software (Version 9.4), unless otherwise noted. Medical History and adverse events will be coding using the current Medical Dictionary for Regulatory Activities (MedDRA) version. Concomitant medications will be coded using the most current version of the World Health Organization (WHO) Drug Reference List.

4.2.3. Methods of Pooling Data

Not applicable to the present study.

4.2.4. Adjustments for Covariates

Statistical models will adjust for the stratification variables as covariates.

4.2.5. Multiplicity

The following multiplicity adjustment approach will be used to strongly control the overall Type I error rate at 0.05 (two-sided) for the primary endpoint and three secondary endpoints.

A hierarchical testing procedure will be used for the secondary endpoints. At each step the test for treatment effect will be considered statistically significant if the p-value is less than or equal

to 0.05 and all previous tests also meet this level of significance. The testing hierarchy is as follows:

1. Primary endpoint: CFB in the NSAA Total Score at Week 52
2. Secondary endpoint: CFB in the Stand from Supine Speed at Week 52
3. Secondary endpoint: CFB in the 10MWT Speed at Week 52
4. Secondary endpoint: CFB in the 4-Stair Climb Speed at Week 52

This method provides strong control of the family-wise error rate at the 2-sided 0.05 level.

4.2.6. Subgroups

Primary and secondary efficacy analyses will be performed within each of the following subgroups based on the FAP:

- Baseline Age (≤ 6.0 years old vs. > 6.0 years old)
- Baseline Time to Stand from Supine (≤ 5 seconds vs. > 5 seconds)
- Region (North America vs. Europe/Asia/Australia)

4.2.7. Withdrawals, Dropouts, Loss to Follow-up

Patients who withdrew from the study will not be replaced.

4.2.8. Missing, Unused, and Spurious Data

For the primary and secondary efficacy endpoint analyses, an MMRM using observed case analysis represents the primary method for handling missing data (as described in [Sections 4.10.1](#) and [4.10.2](#)). Multiple sensitivity analyses on the primary and secondary endpoints which utilize alternative methods of handling missing data are being performed as described in [Sections 4.10.4](#) and [4.10.5](#).

Additionally, the following missing data conventions are being applied:

- For all TFTs, as described in [Section 2.6.2](#), If there are any patients not able to complete the test (reason not done = “subject physically unable to complete test”), a value of 0 will be assigned for the speed of the TFT (i.e., speed in units of task per second). For the time to complete endpoints, a value of 12 seconds will be imputed.

Additionally, as described in [Section 2.6.2](#), if the TFT has a grade of 1 or 2 for 10MWT or stand from supine, or a grade of 1 for the 4-stair climb, the speed will be set to 0 and the time set to 12 seconds.

- As described in [Section 3.1](#), if siblings are enrolled, only one sibling will be included in the Randomized Population. Sensitivity analyses for all efficacy variables will be performed with the both siblings’ values to be used (as described in [Sections 4.10.1](#) and [4.10.2](#)).

4.2.9. Visit Windows

Screening takes place in the 4-week interval prior to first day of study drug (Day 1). Week 6 – 19 visits should be conducted with the study week with a ± 4 -day window. Week 26 – 54 visits have a ± 10 -day window.

Safety follow-up should occur within 2 weeks after the last dose of study drug.

However, visits which occur outside the windows will still be included in the analysis for that visit.

4.2.10. Early Termination Visit

If a patient has an Early Termination visit, the assessments from that visit will be mapped to a scheduled visit using the algorithm presented in Table 4. Note that if the subject has already had the corresponding scheduled visit, the early termination visit data will not be included in summary statistics, but will be included in listings. The listings will show the visit as “Early Termination”, not the corresponding mapped visit.

Table 4: Early Termination Visit Window Algorithm

Study Day of Early Termination Visit	Visit mapping
2 – 136	Week-13 Visit
137 – 227	Week-26 Visit
228 – 318	Week-39 Visit
319 – 364	Week-52 Visit

note: The first day of study drug is “Day 1”.

4.2.11. Baseline

A patient’s baseline value will be most recent non-missing value occurring prior to initiation of study drug. In most cases this will be the value assessed at the Baseline visit. If the Baseline value is missing, the next most recent non-missing value will be used (i.e., in most cases this will be the Screening visit value).

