**APPENDIX 1. SCHEDULE OF ASSESSMENTS**

Study Week(s)	Screen a	BL b	Double Blind, Placebo-Controlled Treatment (Weeks 1 - 52)								Safety F/U c
	-4 - 0	0	6	13	19	26	32	39	45	52/ET d	
Informed Consent/Assent	X										
Site Visit e	X	X		X		X		X		X	
Site Call e, f			X		X		X		X		X
Med History/Demographics	X										
Confirm Eligibility	X	X									
Randomization g		X									
Vital Signs	X	X		X		X		X		X	
Weight	X	X		X		X		X		X	
Height		X				X				X	
Physical Examination	X	X		X		X		X		X	
AEs/Con Meds h	X		Continuous								
12-Lead ECG i	X					X				X	
Cardiac Monitoring j	X					X				X	
Hematology/Chemistry k	X	X		X		X		X		X	
ACTH/Cortisol k		X		X		X		X		X	
Urinalysis	X					X				X	
DNA Sample l		X									
Biomarkers, Gene Expression k		X		X		X		X		X	
NSAA, Stand from Supine, 10MWT, 4-Stair Climb, Muscle Strength m	X	X		X		X		X		X	
PUL n		X				X				X	
Videotape Functional Assessments o	X	X								X	
PODCI p		X								X	
Lateral Spinal Radiography, DXA q		X								X	
Study Drug Questionnaire						X					
Nutritional Guidance r		X									
Drug Dispensation		X		X		X		X			
Drug Accountability				X		X		X		X	
PK (plasma and urine) s				X		X				X	

a Per Investigator's discretion, informed consent, medical history/demographic data and lab assessments may be completed remotely by a qualified medical professional.

b The first day of study drug is "Day 1"; unless otherwise specified, all assessments should be completed within a 4 week window prior to Day 1.

c Safety follow-up should occur within 2 wks. after last dose of study drug. Patients continuing in the open-label extension study are not required to perform the safety follow-up.

d If patient discontinues treatment early, patient will be asked to return for early termination (ET) visit prior to their last dose of study drug. Functional assessments performed within 6 weeks of discontinuing treatment do not need to be repeated at the ET visit. If the ET visit occurs after drug has been discontinued, certain assessments may be omitted per Sponsor discretion.

- e Weeks 6-19 should be conducted within the study week with a  $\pm 4$ -day window. Weeks 26-54 have a  $\pm 10$ -day window.

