4.10.1. Primary Efficacy Analysis

The primary efficacy endpoint is the CFB in the NSAA Total Score at Week 52. NSAA Total Scores and the CFB values will be summarized by treatment group and time point using descriptive statistics.

If a patient initiates corticosteroid therapy or discontinues study treatment, all observations from that patient after these events will be censored from the primary efficacy analyses.

The primary efficacy endpoint analysis will be an MMRM ANCOVA. The MMRM model will include:

- CFB in the NSAA Total Score as the dependent variable
- Variables in the Model

Visit (a categorical variable)	
Treatment (edasalonexent or placebo)	Treatment \times Visit
Region (North America vs. Europe/Asia/Australia)	Region \times Visit
Baseline age (as a continuous variable),	Baseline Age \times Visit
Baseline time to stand from supine (as a continuous variable)	Baseline time to Stand \times Visit
Baseline NSAA score (as a continuous variable)	Baseline NSAA score \times Visit

- Patient as a random effect.

The primary efficacy analysis will test the difference between the edasalonexent versus placebo at Week 52 using this MMRM model.

Sample SAS code for the primary efficacy analysis is provided in [APPENDIX 1: Sample MMRM Code](#).

Descriptive summary statistics including number of patients, mean, standard error, least-square means (LS means), LS means differences, along with the p-values and corresponding 95% CIs

will be provided. Specifically, the primary efficacy endpoint hypothesis test of no treatment difference between edasalonexent and placebo is based on the least-squares means (LS-means) difference and corresponding p-value from the Week 52 visit. The results for the treatment difference for the other visits will also be provided to assess the consistency of treatment effect over different visits.

The repeated-measures analysis will be based on the restricted maximum likelihood method assuming an unstructured covariance structure to model the within-patient errors. A Kenward-Roger approximation will be used for the denominator degrees of freedom. If there is a convergence problem due to the unstructured covariance matrix, a compound symmetry covariance structure will be used to model the within-patient variance; if the compound symmetric covariance structure fails to converge, a variance components approach will be applied.

The primary efficacy endpoint analysis is an observed case analysis, with no imputation of missing data.

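### NSAA and the timed tests are read twice before dosing, but the models use only the last reading: a small missed efficiency, not an error

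*SAP*

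**What the plan says.** Protocol Appendix 1 has one row for "NSAA, Stand from Supine, 10MWT, 4-Stair Climb, Muscle Strength", marked at Screening and again at Baseline. The SAP's schedule (Table 1) marks the same tests at the same two visits. Randomisation follows Screening, so the Screening readings precede treatment assignment.

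SAP 4.2.11 defines baseline as the "most recent non-missing value occurring prior to initiation of study drug" and turns to Screening only when the Baseline-visit value is absent. Protocol 9.1 has the same last-value rule.

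The primary model (SAP 4.10.1) lists one NSAA covariate, "Baseline NSAA score (as a continuous variable"), with its visit interaction, next to region, age and continuous baseline time to stand, each also by visit. The secondary models (SAP 4.10.2) replace baseline NSAA with the one baseline value of the test being analysed. Baseline time to stand follows the last-value rule as well. No sensitivity or supportive analysis in SAP 4.10.4 to 4.10.8 or 5.3 uses both pre-dose readings.

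**The concern.** The NSAA is scored by a clinician, and the timed tests depend on effort. The plan treats evaluator and time of day as sources of variation, since it asks for both to be kept constant for each boy (Protocol 6.3.1 and 6.3.2). A single reading is therefore the boy's true level plus error, and that error weakens the covariate. A second pre-dose reading is already scheduled and would recover part of the loss. Because it precedes randomisation, adjusting for it cannot bias the treatment contrast.

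At stake is the width of the confidence interval. The trial expects about 101 evaluable boys, and the secondary endpoints are tested in sequence after the primary (SAP 4.2.5), so a narrowly missed primary closes all three.

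**Working it through.** **Inputs from SAP 4.1.** 126 boys, 2:1, about 20% dropout: 126 × 0.8 = 100.8, taken as 67:34. "an effect size of 0.625 is assumed", from an "underlying standard deviation estimate of 4.8 in the change from baseline in NSAA score" and a difference of 3.0 (3.0/4.8 = 0.625). The test is run "at a 2-sided type I error rate of 0.05".

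**The plan's own figure.** SAP 4.1 says "the study has approximately 80% power to show a difference between the treatment groups". The t-test noncentrality is 0.625/√(1/67 + 1/34) = 0.625/0.2106 = 2.97, which gives power of 83.6% (84.1% by the normal formula with 100.8 boys). The stated figure is therefore slightly conservative. That is a separate matter.

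**Inputs the documents do not give (assumptions).** r is the correlation between the Screening and Baseline readings (test-retest reliability), taken as 0.90 to 0.95. ρ is the correlation of one reading with the Week 52 score, taken as 0.7 to 0.8. Both readings are assumed equally good.

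**Formula.** Scale each reading and the Week 52 score to variance 1.
- One reading as covariate: residual variance 1 − ρ².
- Mean of two readings: 1 − 2ρ²/(1 + r).
- Variance ratio VR = [1 − 2ρ²/(1 + r)]/(1 − ρ²), below 1 whenever r < 1.

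Example, ρ = 0.8 and r = 0.90: (1 − 1.28/1.90)/0.36 = 0.326/0.36 = 0.906.

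**With time to stand in the model.** The planned model already holds a correlated baseline covariate, which absorbs part of the gain. A simulated single-visit ANCOVA (n = 101) assumed that this covariate correlates 0.6 with each reading and with Week 52. Power below is the t-test at 67:34 with noncentrality 2.97/√VR, taking 0.625 as the effect size under the single-baseline model.

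| ρ | r | VR, formula, NSAA only | VR, mean, time to stand in model | Power (from 83.6%) | VR, two readings entered separately |
|---|---|---|---|---|---|
| 0.8 | 0.90 | 0.906 | 0.92 | 86.6% | 0.93 |
| 0.8 | 0.95 | 0.954 | 0.97 | 84.9% | 0.98 |
| 0.7 | 0.95 | 0.975 | 0.99 | 84.0% | 1.00 |

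The mean does at least as well as separate entry, which spends an extra parameter per visit on two collinear terms.

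**Which value is subtracted.** These ratios apply when the model response is the Week 52 score or, equivalently, change from the same mean. If the response is change from the last value and the mean is the only NSAA covariate, half the difference between the two readings stays in the residual and adds (1 − r)/2. At ρ = 0.8 and r = 0.90 the variance becomes 0.326 + 0.050 = 0.376, against 0.360 under the present plan: a ratio of 1.05, which is a loss. At r = 0.95 it is 0.344 + 0.025 = 0.369, a ratio of 1.02. The response and covariate therefore have to be chosen together.

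**The case against.** The strongest reply is that this is a preference. The last value before dosing is a standard, unbiased baseline, used consistently in both documents, and no error rate is affected. That stands.

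The size is also uncertain. Trained evaluators, the same evaluator where possible and video-reviewed training (Protocol 6.3.1, 6.3.6) favour high reliability, where the gain is under one point. Screening may be the poorer reading: Appendix 1 foresees Screening videos that fail quality control, and Protocol 3.4 recognises practice effects. A practice shift common to all boys does not bias the comparison; learning that differs between boys, or poorer Screening tests, shrinks the gain. All of this stands, and it is why the range starts near zero.

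The power base is also open to question. SAP 4.1 takes 0.625 from the SD of change. If 4.8 is the raw SD of change with equal variances, the planned model already has 87.7% power at ρ = 0.8 (normal formula, NSAA covariate only), and the mean raises it to 89.1% (r = 0.95) or 90.6% (r = 0.90). The pattern is the same from a higher start.

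Two stronger readings should be resisted. A reader might infer that the last-value rule is wrong or biases the result; nothing in the documents supports that. A reader might also infer a variance reduction near 20%. That needs single-test reliability of 0.80 together with a correlation of 0.9 between the error-free baseline and Week 52: (1 − 0.81 × 1.6/1.8)/(1 − 0.81 × 0.8) = 0.280/0.352 = 0.795. It is an extreme pairing, it ignores the other covariates, and the documents give neither value.

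**Conclusion.** The point holds as a missed efficiency. A pre-randomisation reading that is already collected goes unused in every model. The direction of the gain is certain if test-retest correlation is below 1 and the two readings are of similar quality. The size rests on assumptions: reliability 0.90 to 0.95, correlation with Week 52 of 0.7 to 0.8, and time to stand in the model. On these, residual variance falls by about 1% to 8%, and power at 67:34 rises from 83.6% to between 84.0% and 86.6%, provided 0.625 applies to the single-baseline model. Larger gains need noisier tests. The planned analysis is valid as it stands, and the priority is low.

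**What to change.** Keep the last pre-dose value for the defined change-from-baseline endpoint and its descriptive summaries. Before unblinding, pre-specify that the baseline covariate, with its visit interaction, is the mean of the Screening and Baseline readings, or the single reading where only one exists. Apply this to:
- NSAA in SAP 4.10.1;
- the speed of the same test in 4.10.2;
- baseline time to stand in all models.

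State the model response with it. Either use the visit score (or change from that mean), which by randomisation estimates the same treatment difference as change from the last value, or keep change from the last value as the response and leave that value in the model beside the mean. The second option is the same as entering both readings, with the slightly smaller gain shown in the table.

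Carry the same choice into the analyses that reuse the primary model (4.10.4, 4.10.5, 4.10.8 and 5.3) and into the imputation models in 4.10.6, and record it in SAP section 6.

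The cost is SAP wording and modest programming, with no extra visit or test. If the primary model is regarded as settled, the change can be a pre-specified sensitivity analysis instead.

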4.3. Interim Analyses

No interim analyses were planned for this study.

4.4. Patient Disposition

All patients who sign the informed consent will be included in a summary of patient disposition. The number of patients screened, randomized, and dosed in each treatment group will be presented. The number and percentage of patients discontinuing and completing treatment, the number of patients discontinuing before study completion (including reason for discontinuation), and the number of patients completing the study will be presented as well.

The number and percentage of patients in the various analysis populations will be presented separately.

The above information will also be provided in a by-patient listing.

4.5. Demographic and Baseline Characteristics

Demographics, including age at Baseline are considered as a continuous variable, frequency of age by year, age at Baseline (≤ 6.0 vs. > 6.0 years) and Baseline characteristics, including time to stand from supine (both as a continuous and dichotomous variable: ≤ 5 vs. > 5 seconds), treatment with eteplirsen (yes vs. no), and region (North America vs. Europe/Asia/Australia) will be summarized by treatment group and overall, and also listed by patient for the Safety

Population. Baseline NSAA score will also be summarized. No inferential statistical comparisons between groups will be performed.

Note that age (in years) will be derived to the tenths place from the date of birth to the date of randomization. For the patients who do not have a date of birth provided (e.g., patients from Germany) the baseline age will be calculated via the years and months old provided at screening plus the time from the screening visit to the date of randomization.

4.6. Concomitant Medications

Concomitant medications will be listed by treatment and coded using the most current version of the WHO Drug Reference List.

4.7. Medical History

Medical History will be listed and coded by patient using the MedDRA version 21.0.

4.8. DMD-Specific Medical History

DMD-specific medical history, including age at symptom onset and diagnosis, will be listed by patient, and summarized by treatment group and overall for the Safety Population.

4.9. Treatment Exposure and Compliance

Throughout the study, patients and their parents/caregivers will complete a diary documenting study drug administration and diet compliance. For the Safety Population, treatment duration, number of administrations, and compliance (summarized by assessing capsule count) will be summarized by treatment group and overall.

Treatment Duration: Treatment Duration will be the number of days from the patient's first dose until their Week 52 visit. If the patient discontinued from the study and did not have a Week 52 visit the subject's Early Termination visit will be used (note: if the subject does not have an early termination visit, the last visit will be used).

The patient's date of first dose is determined by the study drug administration at baseline:

- If for the baseline visit the "first dose of the day administered in clinic" = "No" (i.e., variable EX.EXPERF= "N") then the date of first dose is the date in the field EX.EXSTDAT (i.e., the "Date of study drug administration").
- Otherwise the date of first dose is the date of the baseline visit.

Expected Average Daily Dose: The expected number of capsules that a patient is to take each day is specified at each visit that the patient receives new study medication (e.g., Baseline, Week 13, Week 26, and Week 39, but there may be distribution at unscheduled visits as well). The daily total of capsules is broken up into morning/afternoon/evening administration. The exact capsule count per dose and the capsule dose strength (i.e., 250 mg or 100 mg) will be provided through the IXRS based on the patient weight at each study visit.

The periods are:

- 1st day patient takes study medication to the day before the Week 13 visit
- Week 13 to the day before the Week 26 visit
- Week 26 to the day before the Week 39 visit

- Week 39 to the day of the Week 52 visit.

Please note the following potential modifications to these periods:

- If the patient discontinues the study early, the corresponding period will end at the date of the early termination visit.
- If the patient has an unscheduled visit where study drug is dispensed the periods will be updated to account for this visit. The following is an example of the update to the algorithm where the patient had an unscheduled visit between the Week 26 and Week 39 visits.
 - 1st day patient takes study medication to the day before the Week 13 visit
 - Week 13 to the day before the Week 26 visit
 - Week 26 to the day before the Unscheduled Visit where study drug was dispensed.
 - Unscheduled Visit where study drug was dispensed to the day before the Week 39 visit.
 - Week 39 to the day of the Week 52 visit.

For each study drug administration period, the daily dose (mg/day) is calculated as:

Daily Dose (mg/day) = expected number of capsules per day × capsule strength

(note: Capsule strength is either 250mg or 100mg).

The average daily dose is calculated by taking the average across the patient's different dosing periods weighted by the number of days in the period.

As such the algorithm is:

Average daily dose (mg/day) =

{Daily dose for 1st day patient takes study medication to the day before Week 13 Period × # of days in this period +

Daily dose for Week 13 to the day before the Week 26 visit × # of days in this period +

Daily dose for Week 26 to the day before the Week 39 visit × # of days in this period +

Daily dose for Week 39 to the day before the Week 52 visit × # of days in this period}

/ {Total # of days summed across these periods}.

Please note the following potential modifications to the algorithm:

- If the patient discontinues the study early, the corresponding period will end at the date of the early termination visit.
- If the patient has an unscheduled visit where study drug is dispensed the periods will be updated to account for this visit. The following is an example of the update to the algorithm where the patient had an unscheduled visit between the Week 26 and Week 39 visits.
 - 1st day patient takes study medication to the day before the Week 13 visit

- Week 13 to the day before the Week 26 visit
- Week 26 to the day before the Unscheduled Visit where study drug was dispensed.
- Unscheduled Visit where study drug was dispensed to the day before the Week 39 visit.
- Week 39 to the day of the Week 52 visit.

Actual Number of Capsules: The number of capsules taken will be based on the “number of used units” from the IXRS data which is provided for each study kit. The total number of capsules taken by a patient will be the sum of the “number of used units” across the study.

Note: the following modification to the IXRS data will be applied. If the following holds:

- Is the Kit present at the Site = “No”
- Date returned by subject = “Missing”
- Discrepancy reason is not “Damaged by Subject”

Then the number of used units will be set to 90. (note: in these situations, the convention was for the site pharmacy to set the “Used Units” to 0 and the “Missing Unit” to 90).

Planned Number of Capsules:

Planned Number of Capsules =

{# of Capsules for 1st day patient takes study medication to the day before Week 13 Period × # of days in this period +

of Capsules for Week 13 to the day before the Week 26 visit × # of days in this period +

of Capsules for Week 26 to the day before the Week 39 visit × # of days in this period +

of Capsules for Week 39 to the day before the Week 52 visit × # of days in this period}.

Please note the following potential modifications to the algorithm:

- If the patient discontinues the study early, the corresponding period will end at the date of the early termination visit.
- If the patient has an unscheduled visit where study drug is dispensed the periods will be updated to account for this visit. The following is an example of the update to the algorithm where the patient had an unscheduled visit between the Week 26 and Week 39 visits.
 - 1st day patient takes study medication to the day before the Week 13 visit
 - Week 13 to the day before the Week 26 visit
 - Week 26 to the day before the Unscheduled Visit where study drug was dispensed.
 - Unscheduled Visit where study drug was dispensed to the day before the Week 39 visit.
 - Week 39 to the day of the Week 52 visit.

Percent Compliance: Percent Compliance calculated as:

Percent Compliance = $100 \times \text{Actual Number of Capsules} / \text{Planned Number of Capsules}$.

